#### 6.2 Exclusion Criteria

- 1. Insufficient understanding of the study by the patient and/or parent/guardian.
- 2. Patients who are currently participating in a randomised clinical trial.

For further details on potential co-enrolment in observational studies and clinical trials see Section 7.6.

#### 7 ENROLMENT

## 7.1 Recruitment and screening

Participants will be identified by the clinical team at each centre, most likely from their regular outpatient clinics. If deemed suitable for prescribing of a new systemic immuno-modulatory treatment, or if the patient has been prescribed a new systemic medication within the last 4 weeks and their pre-treatment outcomes are available, the patient and/or their parent/guardian will be asked if they are willing to participate in the study. A Patient Information Sheet and instructions on how to proceed if they are interested in taking part or finding out more about the study will be given to the patient and/or parent/guardian. They will be provided with the contact details to contact the research nurse if they wish to discuss or need further information. All patients and/or parent/guardian will be provided with a full explanation of the study, before obtaining informed written consent.

Patients can also self-refer to the study (using the details found on the study website or recruitment poster).

The time taken from initial contact and provision of information to obtaining written consent should be sufficient to enable appropriate discussions with the patient / family about the study, explanation of the protocol and procedures.

A patient and/or parent/legal guardian should be provided with the study information during their outpatient appointment and may be approached for consent during this visit if considered appropriate. Where the patient and/or parent/legal guardian feel that they have had adequate time to consider, enough information regarding the study and are happy to proceed, then consent can be sought and screening assessments can be undertaken on the same day as initial contact and provision of information.

Consenting can take place remotely using a postal consent form, by secure electronic mail communication (e.g. via NHS.net), or electronic data capture platform (e.g. REDCap). This consent form should be localised and can either be printed by the site team and posted to the patient, or can be emailed to the patient and returned to the site team with the patient's signature. If there are any queries regarding the study, site staff can address these during a telephone call. For postal consent, two copies of the consent form will be mailed to the participant. After signing both copies, the participant will return one copy in a pre-paid envelope (provided by the A-STAR team) and retain the other for their records. For consent via secure email, the participant will sign and return the form electronically, keeping a digital copy for themselves. When using the electronic data capture platform (REDCap), the consent will be stored within the database, and a copy will be emailed to the participant.

#### 7.2 Baseline visit

The baseline visit of potentially eligible participants will take place following written informed consent to participate. Informed consent can also be taken prior to the baseline visit, and patients will have been provided with verbal and written study information beforehand, providing adequate time to consider the implication of taking part. A copy of the consent and assent forms should be kept in the ISF at the participating site, and the consent process documented in the medical notes. Data from clinical assessments undertaken as part of routine care prior to obtaining consent can be used (i.e. safety blood) for assessing eligibility.

The visit will include:

- a. written informed consent will be obtained from the patient or parent/legal guardian
- b. full medical history, including family history and personal history of co-morbidities (including delayed and immediate allergies), atopic eczema diagnosis and treatment history

- c. alcohol and smoking consumption
- d. assessment of eligibility criteria
- e. review of concomitant medication
- f. physical examination; including clinical phenotyping and eczema severity assessments (can be done by all team members who have completed the relevant training (see A-STAR study website under 'Training Resources') and who the local PI deems adequately experienced to conduct these assessments)
- g. blood pressure at the local investigator's discretion
- h. height and weight
- i. safety bloods. To include full blood count, renal and liver profile, total IgE (if part of routine practice), as well as virology (Hep B, Hep C and HIV) as per local practice.
- j. collection of demographic data
- k. completion of EASI, EASI-50, EASI-75 and IGA and POEM, itch severity (NRS), IDQOL/CDLQI/DLQI, EQ-5D-5L (adults)/EQ-5D-Y (4-16 years' old), RECAP
- I. completion of ACT in patients with diagnosed asthma of ≥ 12 years' old
- m. optional: collection of blood for genetic analysis
- n. optional: collection and storage of bloods samples for mechanistic studies, skin biopsies (≥16 years of age), and tape stripping for cutaneous cytokine analyses as well as sample collection for skin microbiome/metabolite work, using standardised operation procedures across all study participating centres that have the expertise and facilities to take part on this module.

In situations when a patient was recruited within the first 4 weeks after treatment initiation, the baseline visit will be recorded retrospectively, and dated as the day of systemic treatment initiation. This can only occur with all required baseline visit data is available to avoid key data missingness.

#### Baseline 2 (Baseline 3, Baseline 4, etc.) - If switching/restarting systemic treatment

If during participation in the study a patient starts a new systemic immuno-modulatory agent or restarts the same systemic treatment after a decision for discontinuation by the treating physician has been made (excluding short-term breaks in treatment), the patient will have a further 'Baseline' visit and retake all baseline assessments, with exception of family and personal medical history and collection of blood for genetic analyses. Baseline Adverse Events information will also be collected. A new signed Informed Consent will not be required but confirmation of continued consent should be documented in the medical notes. Following this new baseline, visits will be scheduled as per original schedule (Day 1, Week 4, Week 16, and so on). If a patient has simply started on a second systemic agent alongside another, then no baseline visit is required, just 3-monthly visits as per protocol.

## 7.3 Follow up visits

Follow up visits will occur at 4 weeks after the start of systemic immuno-modulatory therapy, 16 weeks and three-monthly thereafter whilst on systemic therapy up to Visit 6 (12 months). Then follow up visits will be every six months (for example: Visit 7 will be at 18 months, Visit 8 will be at 24 months and so on). Once treatment has been stopped, follow ups are also done six-monthly.

If a patient is recruited within the first 2 weeks after treatment initiation, visit 2 will happen at week 4 (±2 weeks), as per usual schedule of events. In situations when patient recruitment occurs 3-4 weeks after treatment initiation, visit 2 assessments will be conducted on the day of recruitment.

Follow up visit procedures:

a. Confirm informed consent status.

- b. Review of co-morbidities and concomitant medication.
- c. Review of systemic therapy (any changes since last visit/current dose) and disease control (number of controlled weeks).
- d. If treatment has been switched: reasons for switching, and outcomes in patients at the point at which the subsequent treatment is initiated.
- e. Reasons if discontinuing (lack of effectiveness, adverse events, patient preference, disease remission, other).
- f. Smoking and alcohol consumption.
- g. Review of adverse events experienced since the previous visit.
- h. Any A&E, hospital, GP or healthcare skin-related visits, and whether due to disease exacerbations, including skin infection.
- i. Days lost from usual activities due to skin disease (e.g. school, work).
- j. Any further phototherapy (TL01, PUVA or other; number of doses).
- k. Physical exam (at the discretion of the treating physician and with their oversight), including weight, and BP.
- I. Safety blood samples are recommended at all study visits.
- m. EASI, -IGA, POEM, itch severity (NRS), IDQOL/CDLQI/DLQI, EQ-5D-5L (adults)/EQ-5D-Y (4-16 years' old), and RECAP.
- n. Completion of ACT in subjects with diagnosed asthma of ≥ 12 years' old\*.
- o. Optional: collection of blood samples, skin biopsies (≥16 years of age), and skin tape strips for mechanistic work and collection of skin microbiome/metabolite samples, using standardised operation procedures across all study participating centres that have the expertise and facilities to take part on this module.\*\*
- \*ACT only done at 16 weeks and 12 months and then every six months.
- \*\*Only done at 4 and 16 weeks, as well as, one year into treatment.

Patients will be followed up for as long as possible, even if they stop treatment. The following target visit windows apply: V2 + /-2 weeks (weeks 2-6), and then +/-4 weeks thereafter, i.e. V3 weeks 12-20, etc. The date of the actual visit will be recorded in the CRF. For patients participating in the bioresource, the target visit windows are reduced to: V2 + /-1 week and V3 + /-1 week with +/-2 weeks in exceptional circumstances.

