During the observation period, participants will be assessed on a regular (3-6 monthly basis) to collect data on disease severity and other clinical outcomes (such as quality of life), adverse events, reasons for potential changes in therapy and key healthcare resource use (e.g. hospitalisations, specialist and GP visits, and drug use). The latter will form part of the health economic feasibility assessment, which will also examine the potential use of HES and CPRD data for health economic evaluation purposes. [The study outcomes are based on the results of a recent international consensus exercise – TREatment of severe Atopic eczema Taskforce (TREAT).]

The first study visit occurs at enrolment (Baseline Visit, V1). V2 and V3 will be scheduled for 4 weeks and 16 weeks and there will be three-monthly visits thereafter while on systemic therapy up to V6. After V6, patients will be seen at 6-monthly intervals.

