#### Recallability:

Identifiable data will also be used by the central study team to contact patients willing to be invited to take part in further research.

Paper CRFs:  If the online data entry platform is temporarily unavailable, alternative data entry on paper will be possible. Paper CRFs will be used for subsequent data transcription to the eCRF. Paper CRFs can also be used as primary source data collection tool. All identifiable data will be kept separate.
Optional participation in a separate bio-analytic module on biomarkers, mechanistic, genetic and pharmacogenetics studies.
Treatment effectiveness:  - Change in EASI (Eczema Area and Severity Index), EASI-50, EASI-75 and IGA (Investigator's Global Assessment)  - Change in POEM (Patient Oriented Eczema Measure) score  - Change in quality of life (DLQI/CDLQI/IDQOL) (Dermatology/Children's Dermatology Life Quality Index)/EQ-5D)  - Change in ACT (Asthma Control Test) score in patients with a diagnosis of asthma  - Disease control as totally or well-controlled weeks  - Drug survival, and long-term control of disease (e.g. time to discontinuation of treatment).  Pharmacovigilance/safety reporting: All (S)AEs will be captured and MedDRA (Medical Dictionary for Regulatory Activities) coded, including malignancy (melanoma, non-melanoma skin cancer, lymphoma), serious infections (e.g. TB), cardiac and CNS disorders. Relationship to studied drugs and any reason for change in treatment dose and/or change to different treatment will be recorded. We will make use of data linkage to available registers (see above).  Cost-effectiveness analysis:  We will calculate the mean costs and assess generic quality of life with the EQ-5D (which is the health benefit measure preferred by NICE), estimated at different follow up times, for each treatment group/pathway to inform the development of an economic model. This will be in adherence to NICE (2013) methods guidance – whose objective is to estimate (i) long-term cost and QALYs for each treatment options, and (ii) incremental cost-effectiveness estimates to assess the value for money of each intervention. Value of information analysis will be used to identify those areas for further research which have the highest return in terms of population health.  Standardised biorepository of blood, leucocytes and serum for genetic and biomarker analyses as well as skin biopsies (>16 years),

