#### 8.3.2 Health economics

There are two stages for the health economic investigations:

- 1. Pilot Phase: Information relating to the health economic component of the study, such as GP visits and attendance at other healthcare professionals, include required time off school or work, due to patients' atopic eczema will be gathered via the eCRF. This will allow us to assess the most relevant healthcare resource utilisation items for participants to record their healthcare contacts and which patient reported health-related quality of life instruments are most appropriate (particularly in the paediatric population). In order to identify the most efficient health economics data collection design, we will explore the feasibility of comparing direct patient reported data versus routine data linkage strategies (e.g. CPRD and HES) versus a mixture of the two. We will evaluate the cost, quality, accuracy and completeness of these data collection strategies for healthcare resource utilisation and health-related quality of life data collected prospectively via the eCRF. Furthermore, we will assess which of these strategies is best to estimate mean costs and patient reported health-related quality of life (including the EQ-5D data, the health benefit measure preferred by NICE) during the study period and for each eczema treatment option. Finally, our results will be used to identify a (health economics) core outcomes set for the assessment of eczema therapies, which can guide the design of the health economics component of future RCTs in eczema.
- 2. Post-Pilot Phase: These data will facilitate the cost-effectiveness assessment of alternative treatment strategies in the patient population recruited in the registry. Long term follow up data will be needed to develop a model-based health economics model describing the disease prognosis, the main clinical events experienced by patients, and associated costs and health related quality of life (HRQoL) implications. This

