# 12.5 Linkage to National Healthcare Data Providers

It is recognised that there is potential for patients intended in the mid to long term to be lost to follow-up or for events to be missed during the data collection process. To mitigate against this risk, the study will link data to relevant datasets held by certain national providers of healthcare data for long term follow up and health economic research. These include Hospital Episodes Statistics (HES), mortality, Clinical Practice Research Datalink (CPRD), and NCRS (National Cancer Registry Service) such as by NHS Digital in England, for long term follow up. This data will supplement that acquired via the dermatology team and provide a more comprehensive picture of each participant's health. PID will need to be used for this purpose; this data will be encrypted and stored, and only the minimum amount of identifiable data will be used as sufficient to provide a robust linkage, often only NHS number (or equivalent outside the UK), DOB, and postcode, avoiding patient name where possible, being transferred to the relevant organisation for the purpose of linkage. The linkage will occur in a secure data environment and only de-identified data will be returned. Although this linkage will not happen immediately, consent of the participants will be sought right from the beginning. Patients can opt out at any time.

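### The visit item that counts healthcare contacts is worded as skin-related while the summary promises resource use without limit by cause, so costs that rest on it could miss care for non-skin drug harm

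*Protocol*

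**What the plan says.** **Promise.** Section 2 of the protocol, under study conduct and schedule, says visits will collect "key healthcare resource use (e.g. hospitalisations, specialist and GP visits, and drug use". No cause is specified. Under cost-effectiveness analysis it adds: "We will calculate the mean costs and assess generic quality of life with the EQ-5D". This is to be done for each treatment group or pathway, to feed an economic model.

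**Collection.** Section 7.3 lists what is asked at follow-up. Item h is "Any A&E, hospital, GP or healthcare skin-related visits, and whether due to disease exacerbations, including skin infection". Item i is "Days lost from usual activities due to skin disease (e.g. school, work". Section 8.3.2 (pilot phase) describes the eCRF information as "GP visits and attendance at other healthcare professionals, include required time off school or work, due to patients' atopic eczema".

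**Other sources and later steps.** Section 8.3.2 continues: "we will explore the feasibility of comparing direct patient reported data versus routine data linkage strategies (e.g. CPRD and HES) versus a mixture". Section 12.5 commits that "the study will link data to relevant datasets held by certain national providers of healthcare data for long term follow up and health economic research", naming HES and CPRD among others. It adds that this linkage lies some way off and that patients may opt out. Section 8.3.2 sets an NHS and Social Services perspective and leaves the detail to a health economics analysis plan that awaits funding.

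**The concern.** The collection item is narrower than the promise. A treatment cost should include the care that the treatment itself causes. If a drug leads to a GP, A&E or outpatient attendance for a renal, liver, blood or infective problem outside the skin, item h as worded does not ask about it.

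Two things are at stake. First, EQ-5D is generic, so it can register the patient's loss of health from such harm while the cost of the related contacts goes unrecorded. The cost comparison would then lean towards the drug with more non-skin harm. Unequal harm is plausible on the protocol's own account: section 3.1 gives renal toxicity as the limit on prolonged ciclosporin use, and most of the adverse event prompts in 8.2(d) are non-skin.

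Second, the pilot phase is meant to find which resource items matter and which collection route is most complete. An item restricted to the skin cannot show whether contacts for drug harm matter.

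**Working it through.** The protocol states no figure on this point, so there is none to reproduce. The check sets the sources side by side and then works out the direction of any bias.

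**Step 1: which described source would count a non-skin GP, A&E or outpatient contact?**

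| Source | Section | What it gives |
|---|---|---|
| Contact item | 7.3(h) | Skin-related contacts, on the natural reading |
| Adverse event review | 7.3(g), 8.2(d) | The event, and whether it led to or prolonged an admission; no count of other contacts |
| Supporting records for adverse events | 10.8 | Admission records and similar, shared to investigate an event |
| Concomitant treatment | 7.5 | All drugs for any condition; no visits |
| Unscheduled visits | 7.3.1 | Returns to the study clinic and admissions for flares; not GP or A&E care elsewhere |
| Linkage | 12.5, with consent under 6.1 criterion 3 | Could supply hospital and GP contacts of any cause; later in time, opt-out allowed |

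Only linkage could fill the gap for contacts without admission. No section names it as the cost source for non-skin care. Section 8.3.2 treats it as one of three options, and section 2 speaks of examining its potential use.

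**Step 2: direction of bias.** For drugs A and B, let
- t = non-skin, drug-related contacts per patient-year that item h does not count,
- c = cost per contact,
- f = share of those contacts recovered from other sources, taken as equal for both drugs.

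Error in the estimated cost difference (A minus B) = −(tA − tB) × (1 − f) × c.

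If tA > tB, the error is negative and A looks cheaper than it is. If f = 1 or tA = tB, the error is zero.

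**Step 3: illustration only.** The protocol gives none of t, c or f. Assume one uncounted contact per event, and borrow the annual rates and rate ratio of 2 from the planning table in 9.3:
- 1/100 against 2/100: 0.02 − 0.01 = 0.01 contacts per patient-year omitted from the difference.
- 10/100 against 20/100: 0.20 − 0.10 = 0.10 contacts per patient-year omitted.

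Each is then multiplied by (1 − f) and by an unknown c. At f = 0.5 the range is 0.005 to 0.05. These figures show how the formula behaves; they do not estimate the bias.

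**Step 4: the pilot comparison.** Suppose patients recall perfectly. A skin-only report would still show fewer contacts than unrestricted GP and hospital data, because the definitions differ. An apparent lack of completeness would mix definition with recall, unless the routine data were first filtered to skin causes.

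**Step 5: lost days.** Days off school or work are not a cost to the NHS and Social Services. The restriction in item i therefore cannot bias the stated cost and is a matter of consistency only.

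**The case against.** The strongest case on the other side has four parts.

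- **Toxicity is recorded.** Every adverse event is reviewed at each visit, with a prompt on admission, and all concomitant drugs are entered. An economic model can attach a cost to each recorded event. This stands in part. It means a reader should not infer that care for drug harm has no recorded trace or a recorded cost of zero. But an event-based cost still needs the number of GP, A&E and outpatient contacts per event, and no described field gives it.
- **Linkage is a commitment.** Section 12.5 says that the study will link, including for health economic research, and agreement to linkage is an inclusion criterion. This also stands, so a reader should not infer that the gap can never be closed. It is weakened by the delay, the opt-out, and the fact that the only example provider is in England while the register also covers Ireland.
- **The cost method is not yet fixed.** The pilot will choose the source and a later plan will set the method. So a reader should not infer that the promised mean costs are biased; the protocol supports only a conditional risk. Deferral does not remove that risk, because a later plan cannot recover from patients what they were never asked.
- **The wording is ambiguous.** In item h, the skin restriction might attach only to the last kind of visit. In 8.3.2, the reference to eczema might attach only to time off. The eCRF itself is not shown. If so, sites may record different things, which is also a reason to reword.

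A reader might also multiply the 9.3 rates by the 12,000 patient-years in 9.4 (12,000 × 0.01 = 120; 12,000 × 0.10 = 1,200) and take 120 to 1,200 as the number of events with missing cost at a rate ratio of 2. The documents do not support this. The rates and the ratio are planning inputs for power, the exposure is a long-term aim, and none of them measures contacts that go uncounted.

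**Conclusion.** The point holds as an inconsistency with a conditional consequence. The only described prospective item that counts healthcare contacts reads most naturally as skin-related, and 8.3.2 points the same way, while the summary sets no limit by cause.

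To the extent that mean costs rest on that item, alone or mixed with linkage, GP, A&E and outpatient contacts from non-skin drug harm are left out. The comparison then favours a drug with more of them. This assumes that such contacts differ between drugs and that other sources do not recover them fully. The size cannot be derived from the protocol. The like-for-like problem in the pilot does not depend on which cost source is finally chosen.

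**What to change.** Reword 7.3(h) to record A&E, hospital, outpatient and GP contacts since the last visit, each with a reason field: eczema or skin; possible drug effect or drug monitoring; other. Align 8.3.2 with the summary. Keep skin-related contacts as a defined subset, so that earlier and later data can be compared, and add a version flag because visits already recorded remain skin-only. For consistency, state whether item i is meant to stay limited to skin disease.

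If the item is not changed, state in 8.3.2 that linkage is the cost source for non-skin care, and label any estimate from the eCRF alone as eczema-related costs. In the pilot, filter the routine data to skin causes before comparing them with patient report.

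The cost is one reworded eCRF item, one added field and matching text in two sections. Patients have slightly more to recall at each visit.

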tape stripping for cutaneous cytokine profiles, and skin swab samples for microbiome work (optional).
Descriptive and exploratory data analyses will be conducted on a 6-monthly basis. All participating centres will receive a summary report of all patients as well as their own.

Version and date of protocol amendments:	V2.0 (26-FEB-2019) V3.0 (09-AUG-2021) V4.0 (01-JUL-2022) V4.1 (12-MAR-2024) V5.0 (08-APR-2025)
---	--

	V1	V1b	V2	V3	V4	V5	V6	
Study visits and assessments	Baseline	Day	4 weeks	16 weeks	6 months	9 months	12 months	Baseline 2,
		1 h					**	3, 4 etc.
	(-28 days)		(+/- 2 wk i )	(+/-4 wk j )	(+/-4 wk)	(+/-4 wk)	and subseq.	(where
							Visits	applicable)
							(+/-4 wk)	***
Informed consent	Х							
Inclusion/exclusion criteria	Х							
Demographics	Х							Х
Personal/family history	Х							
Smoking and alcohol consumption	Х		Х	Х	Х	Х	Х	Х
Atopic Eczema and treatment history	Х		Х	Х	Х	Х	Х	Х
Co-morbidities (including immediate	V		V	V	V	V	V	V
and delayed allergies)	Х		Х	Х	Х	Х	Х	Х
Concomitant medication	Х		Х	Х	Х	Х	Х	Х
Physical examination a	Х		Х	Х	Х	Х	Х	Х
Blood pressure (if applicable)	Х		Х	Х	Х	Х	Х	Х
Treatment (prescribed)	Х		Х	Х	Х	Х	Х	Х
Adverse events			Х	Х	Х	Х	Х	Х
Safety bloods b	Х		Х	Х	Х	Х	Х	Х
EASI, EASI-50, EASI-75	Х		Х	Х	Х	Х	Х	Х
IGA	Х		Х	Х	Х	Х	Х	Х
POEM	Х		Х	Х	Х	Х	Х	Х
Itch severity (numerical rating score)	Х		Х	Х	Х	Х	Х	Х
CDLQI/DLQI/IDQOL c	Х		Х	Х	Х	Х	Х	Х
EQ-5D-5L (adults) EQ-5D-Y (4-15 years old) c	Х		х	Х	х	х	Х	х
ACT c,d	Х			Х			Х	Х
RECAP c	X		Х	X	Х	Х	X	X
Collection of blood for FLG mutation and other genetic analysis (optional) e	х							
Collection and storage of blood samples for mechanistic studies, drug metabolite and trough level analyses (optional) f	Xg		Х	Х			х	х
Skin biopsies (optional, ≥16 years) f	Χg		х	х				
Skin swab samples (optional) f	Xg		Х	Х				
Tape stripping (optional) f	Χg		Х	Х				
Systemic immuno-modulatory therapy start	Λ-	Xh	^	^				
** Follow up will be six-monthly whether	r tha nationts	252.00.4	or off of system	mia tharanu tr	ootmont.	l .	I	

\*\* Follow up will be six-monthly whether the patients are on or off of systemic therapy treatment.

- a Includes height at baseline and weight at all timepoints. For minors, height at all timepoints.

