#### **Biomarker analyses**

Where patients opt into the voluntary bioresource and mechanistic sample collection, venous blood will be collected to obtain serum for metabolic work and biomarker analyses relating to cutaneous and inflammatory disease (e.g. periostin), as well as to isolate and cryopreserve PBMCs for Immunophenotyping.

Blood samples will be collected at baseline, 4 weeks, 16 weeks and 12 months (or at different timepoints if decided by the SMG or SSC upon emerging evidence) using standard phlebotomy techniques.

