#### Skin biopsies and tape strip collection:

Tape strip skin samples can be collected in participants of all ages, and skin biopsies in those ≥16 years of age (≤ 5mm punch) will be taken on 3 occasions both from involved and uninvolved skin for various analyses such as expressed cytokine, RNA, and immunochemical assessment of atopic eczema. The time points of the skin sample collection are subject to change if decided by the SMG or SSC upon emerging evidence.

Not all participating sites will be involved in the collection of skin biopsies and tape strip samples.

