### 11 ETHICAL CONSIDERATIONS

### 11.1 Ethical Considerations

The study will abide by the principles of the World Medical Association Declaration of Helsinki (2013 amendment) and the principles of GCP and in accordance with all applicable regulatory requirements. This protocol and related documents will be submitted for review to HRA and NRES.

There are no major ethical issues with this study, as it is observational in nature. However, the following points have been considered:

- Medications under observation: Whilst all drugs studied have potential side effects, in particular the conventional immuno-suppressive agents, they are used in standard clinical practice. Full information about possible risks and benefits of all medications will be provided to parents and participants and data on adverse events will be collected and monitored throughout the study. In addition, the treatment of severe atopic eczema in participants will not be compromised by participation in the study. The precise risks and benefits of participating in the study will be outlined in patient information sheets, to be formulated with service user involvement.
- Blood testing: The risks of taking blood include temporary discomfort from the needle in the arm, bleeding, bruising, swelling at the needle site and, in rare instances, infection.
- Other tests for those who consent to the participation in the biorepository module (patients can individually opt into these investigations):
- Skin biopsy: skin sample from lesional and non-lesional skin at baseline, V2 and V3. Every biopsy carries the risk of bleeding, discomfort, infection and scarring, and separate consent will be taken for this procedure. Local anaesthetic will be used to numb the skin beforehand, and intolerance reactions might occur but are very rare.
- Tape stripping: this involves several applications of a sticky disc (like Sellotape) to the skin and is not uncomfortable.
- Skin microbiome: taking skin microbiome samples (ideally the area immediately adjacent to and just before the biopsy, if taken). The sampling procedure is non-invasive and easy to perform, similar to taking a conventional skin swab for bacterial culture.
- Consent in paediatric population: Children up to the age of 16 will be eligible for enrolment in the study and age-appropriate Participant Information Sheets (PISs) will be prepared in line with current guidelines. See section 11.2 for further details.

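### A shared footnote in Protocol 7.3 applies the research-blood schedule to skin samples, giving four biopsy occasions where the schedule table, 8.3.3.2 and 11.1 give three

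*Protocol*

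**What the plan says.** Item o of Protocol 7.3 covers several optional samples in one sentence that begins "Optional: collection of blood samples, skin biopsies (≥16 years of age), and skin tape strips for mechanistic work" and goes on to microbiome and metabolite samples. Its only timing is the double-asterisk footnote at the end of the item: "Only done at 4 and 16 weeks, as well as, one year into treatment". The footnote does not distinguish blood from skin.

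The baseline collection is in 7.2 item n: "collection and storage of bloods samples for mechanistic studies, skin biopsies (≥16 years of age), and tape stripping for cutaneous cytokine analyses", followed by microbiome samples.

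Three other places time the skin samples:

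- Section 8.3.3.2, on biopsies and tape strips: "will be taken on 3 occasions both from involved and uninvolved skin".
- Section 11.1, on biopsies: "skin sample from lesional and non-lesional skin at baseline, V2 and V3".
- The schedule table in section 2: the row "Skin biopsies (optional, ≥16 years)" and the rows for swabs and tape stripping are marked at V1, V2 and V3 and are blank at V6 (12 months).

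Research blood is timed separately in 8.3.3.2: "Blood samples will be collected at baseline, 4 weeks, 16 weeks and 12 months". In the schedule table, the row "Collection and storage of blood samples for mechanistic studies, drug metabolite and trough level analyses (optional)" is marked at V1, V2, V3 and V6.

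**The concern.** Section 7.3 is where a site looks for what to do at a follow-up visit. As written, it includes skin biopsy among the optional procedures at one year. The schedule table leaves that cell empty, and the ethics section tells its readers that biopsies are taken at baseline, V2 and V3. The protocol therefore gives two answers to whether a participant aged 16 or over may be offered a further biopsy of involved and uninvolved skin at one year.

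What is at stake is an invasive procedure in an observational register, offered outside the timing stated to ethics reviewers. In the other direction, a site that follows the table would not collect one-year skin samples that 7.3 lists. Estimates and comparisons of the treatments are not at stake.

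**Working it through.** The check is a count of sampling occasions within one treatment course; no sample-size or power formula applies.

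**The protocol's own figure.** The schedule table marks biopsies at V1, V2 and V3: 1 + 1 + 1 = 3. This agrees with the count in 8.3.3.2 and with the three visits named in 11.1.

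**The count under 7.2 and 7.3.** Baseline (7.2 item n) gives 1. The footnote adds week 4, week 16 and one year, which is 3. Total: 1 + 3 = 4.

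**Sources side by side (number of occasions):**

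| Source | Biopsies | Tape strips | Swabs | Research blood |
|---|---|---|---|---|
| 7.2 item n plus 7.3 footnote | 4 | 4 | 4 | 4 |
| Schedule table, section 2 | 3 | 3 | 3 | 4 |
| 8.3.3.2 | 3 | 3 (natural reading) | no count | 4 |
| 8.3.3 | no count | no count | no count | 4 |
| 11.1 | 3 | no visits given | no visits given | no visits given |

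Two things follow.

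1. The blood column agrees throughout. In 8.3.3.2, biomarker blood has four time points and drug-level blood is taken at baseline and three follow-up visits; 8.3.3 counts four blood visits for adults; the table marks four. The footnote's time points are exactly the three follow-up visits of the blood schedule, so the skin samples appear to have been swept into a footnote that fits blood only.
2. The strength of the conflict differs by sample type. For biopsies, three sources disagree with 7.3. For tape strips, the table does, and so does 8.3.3.2 if its count is read as covering both sample types in that sentence. For swabs, only the table does.

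**A lost table cell is an unlikely explanation.** The blood row keeps its V6 mark while all three skin rows lack one, and for biopsies the table's three marks match the running text of 8.3.3.2 and 11.1.

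**After the fix.** With the one-year time point limited to blood, skin samples fall at baseline, week 4 and week 16 (3) and blood at baseline, week 4, week 16 and 12 months (4). Every row of the table above then agrees.

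**The case against.** The best case for the current text has three parts.

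*The footnote is a limit, not a schedule.* It can be read as naming the visits at which any sample of the optional module is taken, leaving the table to say which sample at which visit. One year is then correct, because blood is taken then. This reading is possible but not the natural one: the footnote is attached to an item that names biopsies and makes no distinction among samples, and nothing in the protocol ranks the table above 7.3. What stands is that 7.3 permits a one-year biopsy. A reader might infer that it requires one, which the text does not support, since the whole item is optional.

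*The time points are adjustable.* Table footnote f and 8.3.3.2 let the study committees change them. That allows a later decision; it does not say which of two conflicting texts applies in this version, and the protocol records no such decision.

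*Practice is governed elsewhere.* Collection starts only once laboratory manuals and procedures are in place (8.3.3), and a laboratory manual sets out the collection requirements (8.3.3.4). The manual is not available here and may well settle the visits. A reader might infer that sites already sample differently, or that participants have had biopsies they did not agree to. Neither is shown: differences between sites are not documented, 11.1 requires separate consent for biopsy, and its risk statement is worded to cover each biopsy taken.

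Two further overstatements should be avoided. Section 11.1 does not time tape strips or swabs, so it cannot be cited against 7.3 for those. The extra occasion also should not be turned into a percentage increase in punches, because the protocol does not state how many punches are taken per skin type and participants may decline any of them.

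**Conclusion.** The inconsistency is real and minor. Read literally, 7.2 and 7.3 give four biopsy occasions in a treatment course against three in the schedule table, 8.3.3.2 and 11.1. The difference is one optional occasion, at one year, sampling involved and uninvolved skin in participants aged 16 or over at selected sites. For tape strips and swabs it is likewise four against three, on the narrower support set out in the working.

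The conclusion rests on reading the footnote as applying to everything listed in item o. It does not depend on any assumed number of punches or on uptake.

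A reader might infer that the effectiveness or safety results are affected. They are not: no endpoint in 9.1 or 9.2 uses skin samples, and the one genetic endpoint (*FLG*) needs a single sample that may be taken at any time. The reason to correct the text is that an operative procedure rule reaches beyond the biopsy timing declared in the ethics section.

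**What to change.** Split the 7.3 footnote by sample type, for example: *Blood samples: 4 weeks, 16 weeks and one year into treatment. Skin biopsies, tape strips and skin swabs: 4 and 16 weeks only.* No other section then needs to change.

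The cost is one footnote in the next amendment. The downside is that the one-year skin samples that 7.3 now allows are given up. If the sponsor wants those samples, the footnote can stay, but the schedule table, 8.3.3.2 and 11.1 must then be amended together so that the ethics section describes the one-year biopsy.
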